Research Title: Vitamin D Supplementation Effect In Children With Pulmonary Tuberculosis Treatment: Randomized Double Blind Controlled Trial

Principal Investigator: dr. [name], Sp.A

Expertise: Pediatrics
Position: Doctoral Student

E-mail: [contact]

Institution: Program Pascasarjana Program Studi Doktor Fakultas Kedokteran Universitas Padjadjaran

Institution e-mail: [contact] Sponsor: Individual (Principal Investigator)

Clinical Monitor: Dr. dr. [name], M.H., M.M., FISQua

Investigator teams:

[name]. [name], dr., Sp.A(K), M.Kes Prof.Dr.[name], dr., Sp.A(K), M.Sc Ph.D Dr.[name], dr., Sp.A(K)

Disclaimers: The investigators have no potential conflict of interest

Source(s) of support/funding: No funding or other financial support was received.

Disclosure of relationships and activities: none declared

Ethical issues: The contributing investigators have no potential ethical issues.

Document Last Update Date: 1 June 2021

Summary of Clinical Trial Protocol

Study Description:

This randomized, double-blind control trial with a cohort design was conducted in Bethesda Hospital West Borneo from December 2020 - May 2021. The inclusion criteria were children between 6 to 18 years old, newly diagnosed with pulmonary tuberculosis with vitamin D insufficiency. Diagnosis of the tuberculosis case was based on The Indonesian Pediatric Tuberculosis Scoring System. It consists of history taking and laboratory findings that support tuberculosis common symptoms such as household contact, prolonged fever more than two weeks, non-remitting cough more than three weeks, and decrease body weight, and lymph node enlargement; laboratory findings include Tuberculin Skin Test (TST) and chest X-ray (CXR). Scoring ranges from 0 to 3 for each variable with a total score of more than six is considered as tuberculosis diagnosis. Patients also collect the sputum for gram staining and Xpert MTB/RIF examination. The isolation of Mycobacterium tuberculosis was not done in this study because of limited resources.

Subject selection was determined based on consecutive sampling, namely the order of patients who came to the clinic until the minimum sample size (84 subjects) met the inclusion criteria. The exclusion criteria are children with a history of liver or kidney abnormalities, immunocompromised, and already received vitamin D supplementation. After obtaining written consent, all subjects had their blood specimens drawn 3cc from the brachial vein to measure alanine transaminase (ALT), alkaline phosphatase (ALP), serum active 25-hydroxyvitamin D using the ELISA method. Vitamin D is categorized as deficiency if serum 25-hydroxyvitamin D is below 20ng/mL, insufficiency between 20–30ng/mL, and normal levels above 30ng/mL. In this study, the 95% confidence level (Z α = 1.65 one-sided test) and 80% power test (Z β = 0.84) were selected. The calculation of the sample size above obtained n = 35 people for each group. The total study subjects were added by 20% of the minimum number of samples to compensate for loss-to-follow-up, so the total sample was 84, consisting of 42 patients in the intervention group and 42 patients in the placebo group.

For each subject, the following data were entered into the study database demographic data (name, age, sex), signs and symptoms (fever, cough), Tuberculin Skin Test (TST), Chest X-Ray, and also GeneXpert for Mycobacterium tuberculosis from gastric lavage or sputum induction, liver function test and 25-hydroxyvitamin D level. All results were recorded in a study database following international standards to protect the privacy and personal information.

Subjects were randomly assigned to receive either a 1000IU vitamin D supplement dose or a placebo with an allocation ratio of one to one. Before starting recruitment, the project manager prepared 84 packs of study preparation - 42 packs of the active study drug and 42 packs of a placebo, then generated a randomization sequence using a computer program assigning the terms active or placebo to numbers 1 to 84. The packs were then assigned a randomized number according to this computer-generated randomization sequence.

At recruitment, study staff enrolled patients consecutively according to the order of arrival of patients from number 1 to 84. Study staff who assigned patients to active drugs or placebo did not know the following assignment in the sequence because they did not have access to the study code. Treatment allocations were hidden from patients and research staff. Those who analyzed the data were not covered for group assignments. Monitoring of subjects medication adherence and daily symptoms conducted by using a checklist table filled out by the patient's parents and confirmed check by the researcher during the patient follow-up schedule to the clinic.

All subjects received antimicrobial treatment for tuberculosis drugs in the form of a fixed-dose combination. Patients were reviewed on 14, 28, 42, and 56 days after starting antimicrobial treatment; body weight and height were measured at each time point. After the intensive phase of antimicrobial treatment, patients were monitored monthly. A repeated vitamin D level by ELISA and liver function test were done six months after starting the antimicrobial treatment.

Clinical Trial Process

- a) Administration of intervention (dose regimen, invasive and non-invasive measures, comparison drugs, placebo): Pediatric patients diagnosed with TB and vitamin D insufficiency will be given vitamin D supplementation of 1000IU/day for six months. Giving a placebo in the control group will get one dose of placebo/day for six months. Vitamin D and placebo preparations are prepared in the same colored bottles containing vitamin D or a placebo.
- b) Determination of outcome indicators:
 After six months of treatment, the patient will have his vitamin D level checked.
- c) Interim analysis plan: sputum examination is performed every two weeks during the intensive phase of antituberculosis treatment.
- d) Clinical trial termination procedure:

Parents of patients who refuse to be included in this study can stop the administration of vitamin D supplementation by reporting to the doctor in charge of the service during control at the pediatric outpatient clinic at Bethesda Hospital, West Kalimantan. Patients who do not complete treatment for six months (including unexpected events) will be discontinued from participating in the study and explained to parents that TB treatment is continued but not included in the study, and the test drug package will not be continued.

- e) Estimated research time required for one subject per one course of action: 5 minutes per action of blood and phlegm examination.
- f) Ethical issues (state your opinion on ethical issues in research that may be encountered):
- Respect for someone (respect for human dignity):

Researchers provide information to parents of research to be carried out, including procedures, benefits, risks, volunteering, and data confidentiality. Information is provided so that the subject's parents can determine whether their child can participate in the study or not. Parents are free to make their own decisions. Subjects' parents who voluntarily participated in this study were then asked to express written consent by signing informed consent.

• Beneficence (beneficial) non-maleficence (not harmful):

There is no physical risk to the child who is the subject of the study, but it can cause it to occur. The benefits of this research are not felt directly by the child/parent. However, the willingness to be a subject will be significant to obtain information on routine vitamin D levels in children with tuberculosis. It can be used as input and the essential information to provide vitamin D supplementation in children with tuberculosis. Suppose the examination results reveal a vitamin D deficiency. In that case, the child will receive vitamin D supplementation at no charge to the parents.

• Justice (fairness):

All subjects are treated equally in the study and are given the same opportunity to be included, which is carried out in a fair and balanced manner.

Adverse Event (AE) reporting plan

- a. Recording (Things to be reported): symptoms of side effects of antituberculosis treatment such as jaundice, nausea, and vomiting.
- b. Analysis and procedure of action: the patient will be examined for liver function. If the liver function increases, antituberculosis drugs will be discontinued.
- c. Emergency rescue system: patients who feel there are complaints of nausea, vomiting, and jaundice will go to the Children's Clinic, Bethesda Hospital, West Kalimantan.
- d. Discontinuation of subjects in the study due to adverse events: the administration of antituberculosis drugs will be discontinued, and patients will not be included in the study.

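### Does the one-sided 5% sample-size calculation, with 20% added for loss, leave the trial short of its stated 80% power?

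*Protocol*

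**What the plan says.** The sample size is in the Study Description of the Protocol's summary. The error rates come first: "the 95% confidence level (Z α = 1.65 one-sided test) and 80% power test (Z β = 0.84) were selected". The result follows: "The calculation of the sample size above obtained n = 35 people for each group". The allowance for loss comes last: "The total study subjects were added by 20% of the minimum number of samples to compensate for loss-to-follow-up, so the total sample was 84", split equally as 42 and 42.

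Earlier in the same section, consecutive recruitment is said to run "until the minimum sample size (84 subjects) met the inclusion criteria".

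The text shown gives no effect size, standard deviation, event rates or formula, although it refers back to a calculation. It states no expected loss rate. It does not say whether final p-values or intervals will be one- or two-sided. Under Clinical Trial Process, item b, the only outcome indicator named is the vitamin D level after six months of treatment.

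**The concern.** Three features invite suspicion.

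- **Sidedness.** A one-sided 5% test allows a 5% chance of wrongly declaring benefit. A two-sided 5% test allows 2.5% in that direction. No reason is written down. Pairing a 95% confidence level with 1.65 can also mislead a reader who expects 1.96. If results were then reported with two-sided p-values or 95% intervals, the stated 80% would overstate the power behind them.
- **Loss.** Multiplying by 1.2 is often mistaken for protection against a 20% loss, which would require dividing by 0.8.
- **Minimum.** The word is attached to 84 in one sentence and to the number before the 20% addition in another. A reader may ask which of the two has 80% power.

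If these were real errors, the trial would be smaller than its own target requires and its power claim would be wrong.

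**Working it through.** **Inputs, all from the Study Description:** Zα = 1.65 (one-sided), Zβ = 0.84, 35 per group, 20% added, 42 per group, 84 in total.

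**1. The plan's own figures.**
- 35 × 1.20 = 42 per group, and 2 × 42 = 84. This reproduces exactly.
- The upper tail beyond 1.65 is 0.0495, so 1.65 is the right value for a one-sided 5% test.
- The 35 cannot be rebuilt independently, because no effect size is shown. It can only be taken as given. Under a normal approximation, 35 per group with these error rates fixes the expected test statistic at 1.65 + 0.84 = 2.49. For a comparison of means (an assumption) this is 2.49 × √(2/35) = 0.595 SD. Recovering 80% from this value is circular, so it does not verify the 35.

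**2. Power at other sizes and for both tests.** The expected statistic at n per group is 2.49 × √(n/35), and power = Φ(expected statistic − critical value).

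| n per group | Expected statistic | One-sided 5% (1.65) | Two-sided 5% (1.96) |
|---|---|---|---|
| 33.6 | 2.440 | 78.5% | 68.4% |
| 35 | 2.490 | 80.0% | 70.2% |
| 42 | 2.728 | 85.9% | 77.9% |

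If 35 was rounded up from just over 34, the two-sided values rise to 71.4% at 35 and 79.0% at 42. With a t-test they are 69.0% and 76.9%. A two-sided 5% test with 80% power would need 35 × (2.80/2.49)² = 44.3, so 45 per group.

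The one-sided column belongs to the test that the Protocol selects. It meets 80% at 35 and exceeds it at 42. The two-sided column belongs to a test that the Protocol never mentions. The difference between the columns is 9.8 points at 35 and about 8 points at 42.

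**3. Loss.** Going from 42 to 35 is a loss of 1 − 35/42 = 16.7%, or 7 per group. Had the Protocol stated an expected loss of 20%, 35/0.80 = 43.75, so 44 per group, would have been needed. It does not state one. It says that 20% of the minimum number is added, and that is what was done. Even at a true 20% loss, 42 × 0.80 = 33.6 per group remain and one-sided power is 78.5%, about 1.5 points below target.

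**4. Which number the 80% belongs to.** The order of the sentences settles it: error rates are chosen, 35 per group is obtained from them, and 20% is then added for loss. The 80% belongs to 35 per group. The 84 is the enrolment target.

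**The case for a change.** The strongest counter-argument is that sidedness was decided in the Protocol itself, so an unseen SAP cannot excuse it. If that SAP reported two-sided results, the 80% would stop applying. The power figures need no knowledge of the effect size and stay below 80% under every variant tried for a comparison of means. Enrolment of 42 is 3 short of the 45 that a two-sided test needs, even with no loss. Patients who do not complete six months are also taken out of the study, so some loss is likely.

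The arithmetic stands. So does the warning that the 80% must not be attached to a two-sided result, and it is true that the text shown gives no reason for one side. What does not follow is that the plan is wrong. The consequence is conditional on two-sided reporting, and nothing in the document says that will happen. The calculation that the text refers back to is not shown, so a reason may have stood there; this cannot be settled either way. Many statisticians would prefer a two-sided 5% test, but for a supplement compared with placebo on the level of that same vitamin, a directional hypothesis can be defended. A missing rationale is missing detail, and a preference for the other convention does not show an error.

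**Conclusion.** The concern does not hold. The Protocol declares a one-sided 5% test, uses the critical value that fits it, attaches 80% power to 35 per group, and adds the 20% that it says it adds. No step contradicts another, and the design is not shown to miss its stated power. The figures of about 70% and 78% describe a different test. Moving to that test would halve the false-positive rate for benefit, from 5% to 2.5%, at a cost of about 8 to 10 points of power. That is a trade-off on which reasonable statisticians differ.

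The limit of 16.7% on the loss covered is a consequence of the stated rule and contradicts nothing, because no expected loss rate is given. Calling 84 the minimum is loose wording that changes no result.

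This conclusion takes the 35 as correctly calculated, since its effect size is not shown, and uses a normal approximation. It would need another look only if the analysis turned out to be two-sided while still relying on the 80%.

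### Does adding 20% to 35 per group leave the trial short of its own minimum after loss to follow-up?

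*Protocol*

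**What the plan says.** All the figures stand in the Protocol, Summary of Clinical Trial Protocol. The error rates come first: "the 95% confidence level (Z α = 1.65 one-sided test) and 80% power test (Z β = 0.84) were selected". The result is then given: "The calculation of the sample size above obtained n = 35 people for each group". The allowance follows: "The total study subjects were added by 20% of the minimum number of samples to compensate for loss-to-follow-up". The paragraph ends with 84 children, 42 in each arm.

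Two other sentences in the same summary use the enlarged number. Consecutive recruitment runs "until the minimum sample size (84 subjects) met the inclusion criteria", and the project manager "prepared 84 packs of study preparation - 42 packs of the active study drug and 42 packs of a placebo".

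Two later places describe how children leave the trial. Item d of Clinical Trial Process says: "Patients who do not complete treatment for six months (including unexpected events) will be discontinued from participating in the study". Item d of the Adverse Event reporting plan says of children stopped for adverse events that "patients will not be included in the study". The document gives no expected rate of loss and describes no replacement of children who leave.

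**The concern.** Statisticians look for this pattern because it is a common mistake. To keep n evaluable subjects when a proportion d of those enrolled is lost, one enrols n/(1 − d). Multiplying by (1 + d) gives a smaller number and does not restore n after that loss. Here 35 × 1.2 = 42, whereas 35/0.8 = 43.75, so 44 per group.

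The setting adds weight. The percentage is there to compensate for loss to follow-up, so it is natural to read it as the expected loss. Children who do not complete six months leave the study, exactly 84 packs exist, and nobody is replaced, so the allowance is all that protects the 35. The label minimum is also attached to 84 in one sentence and to the number before enlargement in another. If the 20% really were a forecast of loss, the trial would end below its own minimum and below its stated 80% power.

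**Working it through.** **Inputs** (Protocol, Summary of Clinical Trial Protocol): 35 per group; Zα = 1.65, one-sided; Zβ = 0.84; addition of 20% of the minimum; 42 per group, 84 in total; 1:1 allocation.

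**Step 1. Reproduce the plan's figure.** The rule is the minimum plus 20% of the minimum.

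- Per group: 35 + 0.20 × 35 = 35 + 7 = 42.
- In total: 70 + 0.20 × 70 = 70 + 14 = 84.

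Both match the document exactly.

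**Step 2. What loss this covers.** 42 per group can lose 7 and keep 35: 7/42 = 16.7%. This follows from two numbers printed in the same paragraph.

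**Step 3. The alternative reading.** Suppose, although the Protocol does not say so, that 20% of those enrolled are lost.

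- Remaining: 42 × 0.8 = 33.6 per group, which is 35 − 33.6 = 1.4 below the minimum.
- Enrolment that would keep 35: 35/0.8 = 43.75, so 44 per group and 88 in total. That is 2 more per group and 4 more overall.

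**Step 4. Effect on power.** If the test statistic grows with the square root of n, and 35 per group gives the planned power, then

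power(n) = Φ((1.65 + 0.84) × √(n/35) − 1.65).

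The effect size and standard deviation cancel, so none has to be assumed.

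| Loss from 42 | Remaining per group | One-sided power |
|---|---|---|
| 10% | 37.8 | 82.6% |
| 15% | 35.7 | 80.6% |
| 16.7% | 35 | 80.0% |
| 20% | 33.6 | 78.5% |
| 25% | 31.5 | 76.2% |

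At 20%: 2.49 × √(33.6/35) − 1.65 = 2.440 − 1.65 = 0.790, and Φ(0.790) = 78.5%. In whole children, 34 per group gives 78.9% and 33 gives 77.9%.

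**Step 5. How firm 78.5% is.** The formula, effect and standard deviation behind the 35 are not in the text at hand, so the figure assumes that 35 gives 80% with nothing to spare. If 35 was rounded up from 34.01, the same calculation with 34.01 in place of 35 gives 79.5% at 33.6 per group. The loss of power on the unfavourable reading therefore lies between about 0.5 and 1.5 percentage points.

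**Step 6. Does the document commit itself to surviving a 20% loss?** The enlargement sentence takes its percentage of the minimum, not of the enrolled number. The two passages on children leaving the study describe the attrition for which the allowance exists. They state no rate and do not suggest one above 16.7%.

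**The case for a change.** The best case for the concern is that the only stated purpose of the 20% is loss to follow-up and no other rate appears, so many readers will infer that the design tolerates a 20% loss. It does not: that would take 44 per group. Losses do reduce the evaluable number, and no replacement is foreseen. The word minimum is also used inconsistently: if 84 were the minimum, adding 20% could not give 84.

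Part of this stands. The arithmetic for a 20% loss is right, the Protocol could have stated the tolerated loss of 16.7% outright, and calling 84 a minimum is loose.

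None of it makes a defect. The inference to a 20% loss rate is the reader's; the text states an addition and names its base. The tolerated loss can be read off from 35 and 42, so nothing is hidden. The loose label does no harm, because the same paragraph sets out 35 per group, the addition and 84, while recruitment and pack preparation both run on 84 without ambiguity.

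**Conclusion.** The concern fails. The Protocol states a rule, applies it correctly and reaches 84; it contains no claim about a 20% loss that 84 could contradict. The shortfall appears only if a loss rate is supplied from outside the document. Even then it amounts to 1.4 children per group and at most about 1.5 percentage points of one-sided power, with 80% kept for any loss up to 16.7%. Nothing the trial does or can conclude depends on it.

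This rests on taking the enlargement sentence as written and, for the power figures only, on 35 per group giving about 80%, which cannot be checked from the text at hand. A stated expectation that 20% of enrolled children would be lost would make the criticism correct, though still small.

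### The protocol's one sentence on analyst masking most naturally says the analysts knew the groups; clarify it and, if analysis is still to come, lock the data before the arm code is released

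*Protocol*

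**What the plan says.** In the Protocol, under Study Description, the paragraph on recruitment says that staff who assigned patients had no access to the code. It continues: "Treatment allocations were hidden from patients and research staff". The next sentence is: "Those who analyzed the data were not covered for group assignments".

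Other text that bears on the point:

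- **Who made the list (Study Description).** "Before starting recruitment, the project manager prepared 84 packs of study preparation", and then "generated a randomization sequence using a computer program assigning the terms active or placebo to numbers 1 to 84". The protocol does not say who analyses the data.
- **Removals during conduct.** Clinical Trial Process, item (d): "Patients who do not complete treatment for six months (including unexpected events) will be discontinued from participating in the study". Adverse Event reporting plan, item (d), on discontinuation for adverse events: "patients will not be included in the study".
- **Outcome (Clinical Trial Process, item (b)).** "After six months of treatment, the patient will have his vitamin D level checked". The Study Description says this is measured by ELISA.
- **Dates.** The Study Description puts the trial in December 2020 to May 2021, in the past tense. The document was last updated on 1 June 2021.

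**The concern.** The protocol protects patients and staff from knowing the arm, then appears to say that this protection was not extended to the people who analysed the data. That is a statement about who knew what. It is not detail a protocol would normally leave to a SAP, although a SAP not shown here might add to it.

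People who know the arm can be influenced, even without intent, when they resolve queries, treat a value as outlying, handle a missing value or confirm who is in the analysis set. With 35 patients per group required and 42 planned, each such decision has some weight. A reader of the results also cannot tell from this sentence whether the analysis was masked.

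**Working it through.** The protocol gives no figure for this point, so the check is mainly textual. Two short calculations then show what coded or unlabelled data would and would not hide.

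**1. Reading the sentence.** It directly follows a sentence on hiding allocations, so *not covered* most naturally means *not masked*. A weaker reading, that analysts were not given the assignments, is possible in translated prose. No other text masks the analysts, codes the arms or says when the code is broken.

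**2. Against the preceding sentence.** The protocol does not say whether analysts are research staff. If they are, one sentence hides allocation from them and the next says they were not masked. If they are not, the two sentences are compatible.

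**3. Against the removal rules.** Non-completers and patients stopped for adverse events are taken out by rule during conduct, when research staff are stated to be masked. These removals are therefore not shown to be analysts' choices. What remains exposed is cleaning, missing or outlying values and confirmation of the final set.

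**4. Is the analysis finished?** The wording is past tense. Yet 1 December 2020 + 6 months = 1 June 2021, which is the last-update date. Six-month values of anyone who started later would fall after it. The document does not settle the matter.

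**5. How long would A/B codes hide the arms?** The Study Description states: "the 95% confidence level (Z α = 1.65 one-sided test) and 80% power test (Z β = 0.84) were selected", with 35 per group. Assume the sample size was computed for the six-month vitamin D level (the formula is not shown). Under a normal approximation, the coded arm with the better mean is the active arm with probability Φ(k × (Zα + Zβ)), where k is the true effect divided by the targeted effect.

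- Zα + Zβ = 1.65 + 0.84 = 2.49
- k = 1: Φ(2.49) = 0.994
- k = 0.5: Φ(1.245) = 0.893
- k = 1.5: Φ(3.735) = 0.9999
- At 42 per group, multiply the argument by √(42/35) = 1.095: k = 1 gives 0.997 and k = 0.5 gives 0.914

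A coded arm variable therefore stops hiding the arms once the outcome is compared by code.

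**6. How much do unlabelled values reveal?** Under the same assumption, the standardised difference implied by 35 per group is d = √(2 × 2.49² / 35) = 0.595. A random active value exceeds a random placebo value with probability Φ(0.595/√2) = Φ(0.42) = 0.66. Single values without labels carry some information on arm, but far less than a comparison of group means.

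Neither calculation measures a bias in this trial.

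**The case against.** The strongest case on the other side is that this is mostly a wording query. The sentence may be a translation slip. If the analysis is done and was unmasked, the protocol already says so, if clumsily. Only if analysts are unmasked and the analysis is pending is there a design change to make, and the past tense points the other way. The route to harm is also inferred: the protocol does not say that analysts clean the data or settle the analysis set, and a SAP may fix rules for both. Finally, the outcome is a laboratory measurement, which leaves little room for bias in assessment.

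Much of this stands. It is why clarification comes first, why the design change is conditional and why the point is minor. It does not remove the point, because as written a reader cannot tell whether the analysis was masked, and the natural reading is the weaker choice.

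It might also be objected that an unfunded project led by a doctoral student lacks people for a separate list holder. That does not stand. The project manager already generates the list, so keeping that person out of the analysis needs no new staff.

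Three stronger inferences are tempting and unsupported:

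- **That the sentence contradicts the double-blind label.** The text applies concealment to patients and research staff. A conflict arises only if analysts are among the latter, which is not stated.
- **That analysts chose exclusions knowing the arm.** The stated removals are made by rule during conduct.
- **That the result is biased by a calculable amount.** One can simulate someone deliberately dropping unfavourable patients, but nothing in the document suggests this. The allowance for loss to follow-up is not evidence of it either.

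**Conclusion.** The point holds as a minor one. On its most natural reading, the protocol says the analysts knew the groups, and nothing else in it masks them. The sentence conflicts with its neighbour only if analysts count as research staff. Confidence is medium, because the wording is loose and the document does not settle whether the analysis is finished.

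The size of any bias cannot be computed from the document. The gain from masking is modest: settling decisions without arm labels narrows the route for bias but does not close it, given the 0.66 above. The 0.994 bears on timing only: the arm code should be withheld until the data are settled. Both figures rest on the assumption that the sample size was computed for the six-month vitamin D level.

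**What to change.** First state whether the analysts knew the groups and whether they are among the research staff. Then:

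- **If analysis is still to come,** replace the sentence with: *Data cleaning, handling of missing or outlying values and the analysis set are settled and locked on data without any arm variable. The arm code is released to the analysts only after that lock. Whoever holds the randomisation list, including the project manager, takes no part in these decisions or in the analysis.*
- **If analysis was done unmasked,** do not rewrite the sentence as if it had been masked. Disclose it plainly and say whether those who decided exclusions knew the arm.
- **If the analysts were masked,** correct the sentence.

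The cost is a small delay before arm labels are released and one person kept out of the analysis. Sample size, alpha and power do not change. If the analysis is already done, the cost is a short, clear disclosure.

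### Children who stop treatment early leave the study before the only scheduled repeat vitamin D and liver tests, so the six-month comparison is one of completers only

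*Protocol*

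**What the plan says.** Four parts of the protocol bear on this point.

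- **Removal for not completing** (Clinical Trial Process, item d): "Patients who do not complete treatment for six months (including unexpected events) will be discontinued from participating in the study". The same sentence adds that it is "explained to parents that TB treatment is continued but not included in the study, and the test drug package will not be continued".
- **Removal for an adverse event** (Adverse Event reporting plan). Item a records "symptoms of side effects of antituberculosis treatment such as jaundice, nausea, and vomiting". Item b has such a child's liver function tested and continues: "If the liver function increases, antituberculosis drugs will be discontinued". Item d concludes that "the administration of antituberculosis drugs will be discontinued, and patients will not be included in the study".
- **Timing of the outcome** (Study Description): "A repeated vitamin D level by ELISA and liver function test were done six months after starting the antimicrobial treatment". Clinical Trial Process, item b, names the vitamin D level after six months as the outcome indicator. The visits on days 14, 28, 42 and 56 list weight and height. Monthly monitoring afterwards lists no vitamin D or liver test.
- **Expected losses** (sample-size paragraph): "The total study subjects were added by 20% of the minimum number of samples to compensate for loss-to-follow-up", which takes 35 per group to 42.

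The protocol describes no study measurement in a child after removal.

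**The concern.** Removal happens after randomisation and can depend on how the child is doing. If it differs between arms and is related to the outcome, the children compared at six months are no longer the randomised groups, and their difference mixes treatment effect with selection. Even without that, the comparison answers a narrower question: the effect in children who completed six months, not the effect of assigning supplementation.

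For liver function the dependence is written into the plan, because a raised liver test is itself the route to removal. Any six-month liver comparison is then made without the children whose raised test led to a stop.

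This is a rule about which data are collected. An analysis plan may name an all-randomised set or an imputation method, but it cannot produce a six-month sample that staff were not asked to take.

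The two removal rules also conflict. The termination procedure covers unexpected events and tells parents that TB treatment goes on; the adverse-event rule says the antituberculosis drugs stop. A child stopped for an adverse event falls under both.

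**Working it through.** **1. Who has a six-month value?**

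| Child | What the protocol directs | Six-month tests provided for? |
|---|---|---|
| Completes six months | Stays in the study | Yes |
| Does not complete, any reason | Leaves the study, pack stopped | No |
| Drugs stopped for an adverse event | No longer included | No; only the earlier symptom-triggered liver test |

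The six-month comparison therefore contains completers only. Weight, height, sputum and recorded symptoms from before removal may still exist.

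**2. The plan's own allowance.** 35 × 1.20 = 42 per group, and 2 × 42 = 84, which matches the protocol. The plan thus provides for up to 42 - 35 = 7 losses per group, or 7/42 = 16.7%.

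**3. Illustration of selection bias (leaving rates and correlations are assumptions).** Suppose a fraction p of an arm leaves, and leaving has correlation ρ with a standard normal outcome. The mean of those who stay then shifts by -ρ·φ(z)/(1 - p), where z is the (1 - p) normal quantile. The rates used, 25% on active and 8.3% on placebo, average to the 16.7% allowance.

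For ρ = -0.5 (children with low values are more likely to leave):

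- active: 0.5 × 0.3178/0.75 = +0.212 SD
- placebo: 0.5 × 0.1533/0.917 = +0.084 SD
- bias: 0.212 - 0.084 = +0.128 SD

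The rejection rates come from two separate simulations of 20,000 trials, with 42 per arm, no true effect and a one-sided 5% t-test:

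| Leaving, active v placebo | ρ | Bias (SD) | Rejection rate |
|---|---|---|---|
| 25% v 8.3% | -0.5 | +0.13 | 13.3% to 14.1% |
| 25% v 8.3% | -0.2 | +0.05 | 7.7% to 7.8% |
| 25% v 8.3% | -0.1 | +0.03 | 6.3% to 6.5% |
| 25% v 8.3% | +0.5 | -0.13 | 1.3% to 1.4% |
| 16.7% v 16.7% | -0.5 | 0.00 | 4.8% to 5.1% |

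**4. A simpler check.** Let D be the completers' mean minus the removed children's mean, in SD, and q the fraction removed.

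- Same D in both arms: bias = (q_active - q_placebo) × D. With 20% v 5% removed, D = 0.25, 0.5 and 1.0 gives 0.04, 0.075 and 0.15 SD.
- Equal removal of 16.7%, with D present in the active arm only: bias = 0.167 × D, or 0.04, 0.08 and 0.17 SD. Equal numbers removed are therefore not enough if different kinds of children leave in the two arms.
- With 35 per group the standard error is √(2/35) = 0.239 SD. A bias of 0.10 SD in favour of active raises the one-sided error to 1 - Φ(1.645 - 0.10/0.239) = 11%.

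**5. Completers against all randomised.** Suppose leavers in the active arm return to placebo-like levels. The all-randomised difference is then (1 - q) times the completers' difference, so the completers' figure is larger by 1/(1 - q) - 1:

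- 7 of 42 leave: 42/35 - 1 = 20%
- 4 of 42 leave: 42/38 - 1 = 10.5%
- 8 of 42 leave: 42/34 - 1 = 23.5%

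This is a change in the quantity estimated, not a false-positive risk.

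**The case against.** The case on the other side has five parts.

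- **The figures are assumed.** Neither 25% v 8.3% nor a correlation of -0.5 comes from the protocol. Both arms receive the same TB drugs under the same removal rule, and allocation is hidden from families and research staff, so a threefold difference in removal is not an obvious expectation. This stands. The figures show what could happen, not what did. Concealment does not deal with the change of estimand or with removal triggered by a liver result.
- **The outcome-dependent route concerns liver tests, while the named outcome indicator is vitamin D.** Also correct: no text links the adverse-event trigger to the 25-hydroxyvitamin D level, and no between-arm liver comparison is formally defined. The liver argument applies to the repeat test if the arms are compared on it.
- **Some data survive.** Children stopped for a raised liver test have that result, and it can be counted by arm. Early weight, height and sputum data also remain. The gap is therefore confined to the six-month 25-hydroxyvitamin D and liver values.
- **The analysis set belongs in the SAP, and none is shown.** Leaving participation does not mean that collected data are deleted. That is fair for the choice of set, but not for the missing six-month samples.
- **The termination rule could be read as general and the adverse-event rule as its exception.** Possibly, but the general rule explicitly takes in unexpected events, so the overlap is real and needs a sentence to resolve it.

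**Conclusion.** The concern holds. As written, the protocol gives the six-month 25-hydroxyvitamin D and liver values in completers only, and what is lost cannot be restored at analysis. That conclusion rests on the text alone.

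The size and direction of any bias cannot be derived from the document. Under the assumed scenarios it runs from -0.13 to +0.13 SD, and it is nil when leaving is equal and equally related to outcome in both arms. Separately, if the 16.7% loss allowance were used up and active-arm leavers lost the benefit, the completers' difference would exceed the all-randomised difference by 20%. Because the rule governs the only named outcome indicator, it must be fixed.

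**What to change.** 1. Separate stopping the study pack from leaving the study. Unless consent is withdrawn, obtain the planned six-month 25-hydroxyvitamin D and liver tests in every randomised child.
2. Make the main analysis all randomised children by assigned arm, with completers as a sensitivity analysis.
3. Report removals and adverse events by arm with reasons, including liver results found through the symptom-triggered test.
4. Reconcile item d of the termination procedure with item d of the adverse-event plan on whether TB treatment continues after removal.
5. For samples already lost, analyse all available data as randomised, report removals and recorded events by arm, and add missing-data sensitivity analyses. The protocol says the trial "was conducted in Bethesda Hospital West Borneo from December 2020 - May 2021", so this may be all that remains possible.

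**Cost.** For a child still in follow-up: revised wording and the effort of bringing back those who stopped. For a finished trial: analysis and reporting only.

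The estimate will be smaller if leavers lose the benefit, and this affects power. The protocol shows no effect size. Under an assumed two-means formula, 35 per group implies √2 × (1.65 + 0.84)/√35 = 0.595 SD. Measuring all 42 per group gives about 86% power if that effect is undiluted. If 7 active-arm leavers lose the benefit, the effect is 0.595 × 35/42 = 0.496 SD and power is Φ(0.496/√(2/42) - 1.645) = Φ(0.63), about 73.5%.
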